3. OBJECTIVES

- To provide clinical management and, if required, treatment to subjects who at their concluding HPV-015 study visit displayed normal cervical cytology but tested positive for oncogenic HPV infection or who were pregnant at their concluding visit of the HPV-015 study so that no cervical sample could be collected.

Refer to Section 4 **Error! Reference source not found.** for the definition of the study endpoints.

4. ENDPOINTS

- Occurrence of positive oncogenic HPV DNA results in cervical samples by HPV DNA testing (Hybrid Capture® II test [HCII]).
- Occurrence of cervical cytological abnormalities in cervical samples by ThinPrep® PapTest.
- Occurrence of referral to colposcopy.
- Occurrence of referral to treatment.

5. STUDY POPULATION

The study population will contain a subset of HPV-015 study enrolled in HPV-062 study

- Subjects who displayed normal cervical cytology but tested positive for oncogenic HPV infection at their concluding HPV-015 study visit.
- or
- Subjects who were pregnant at their concluding HPV-015 study visit were not able to provide a cervical sample.

HPV-062 -Total cohort

The HPV-062 cohort includes the HPV-015 subjects

- who conclude their participation in the HPV-015 study at Visit 9, Visit 11 or at the last study visit in HPV-015 study displayed normal cervical cytology but tested positive for oncogenic HPV infection

or

FORM-9000026972-01 Statistical Analysis Plan Template
Effective date: 01 June 2014
GSK SOP Reference: SOP-9000026972
Form Owner: VVHS Biometrics, PPD

01June2014

Page 9 of 13

Statistical Analysis Plan	
Study alias & e-track number(s): HPV-062 EXT:015 (113617)	

- who were pregnant during HPV-015 study so that no cervical sample could be collected at that visit.
- who attend any visit in this study.

The list of applicable elimination codes for this cohort

Cohort	Elimination codes	Eli Type
HPV-062 -Total cohort	900,1500	MA

MA: Main analysis

6. STATISTICAL METHODS

The analysis will be performed on the HPV-062 Total cohort

6.1.1. Analysis of demographics

Demographic characteristics (age, race and gender), withdrawal status will be summarised using descriptive statistics:

Age: Age of a subject is computed by considering the date of birth and date of the first visit in this study for that subject. Age of a subject was computed as the time interval between two dates in specified time unit.

- Frequency tables will be generated for categorical variable such as race and gender.
- Mean, median, standard deviation will be provided for continuous data such as age.

The distribution of eligible subjects among the study sites will be tabulated.

6.1.2. Descriptive analysis of clinical management

For each visit and overall:

- Results of oncogenic HPV DNA tests.
- Results of cervical cytology tests.
- Referrals to colposcopy, if required.
- Referrals to treatment according to local medical practice, if required.

Statistical Analysis Plan	
Study alias & e-track number(s): HPV-062 EXT:015 (113617)	

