10.5. Conduct of analyses

Any deviation(s) or change(s) from the original statistical plan outlined in this protocol will be described and justified in the final study report.

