10.6.4. Descriptive analysis of safety

For each subject and overall:

- Results of oncogenic HPV DNA tests.
- Results of cervical cytology tests.
- Referrals to colposcopy according to management algorithm, if required.
- Referrals to treatment according to local medical practice, if required.
- All fatal SAEs occurring throughout the study period.
- All SAEs assessed as being possibly related to study participation occurring throughout the study period.
- All SAEs assessed as being possibly related to GSK products occurring throughout the study period.
- Withdrawal from the study due to AEs or SAEs.

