At each visit, a gynaecological examination will be performed and cervical liquid-based cytology samples will be collected for cervical cytology examination and oncogenic HPV DNA testing, if the cytology reading is normal or ASCUS.

The presence of oncogenic HPV infection will be determined by the Hybrid Capture® II (HCII) test, which detects HPV DNA types 16, 18, 31, 33, 35, 39, 45, 51, 52, 56, 58, 59 and 68 [Vernick, 2003, Digene Corporation 2002]. Cervical cytology examination will be performed using the ThinPrep®Pap test.

Continued study participation as well as further referral/treatment will be based on the test results from each visit, and will be aligned with the clinical management algorithm which is aligned with the 2009 American Society for Colposcopy and Cervical Pathology (ASCCP) guidelines for use of HPV DNA testing as an adjunct to cytology for cervical cancer screening in women 30 years or older.

The following clinical management algorithm will be applied, refer to [Figure 3](#).

- Subjects with normal cervical cytology and who are oncogenic HPV DNA negative, will end their participation in the study.
- Subjects with normal cervical cytology, but who are oncogenic HPV DNA positive in one single test, will be asked to return at the next study visit.
This outcome will only be applicable to subjects who were pregnant at their concluding HPV-015 study visit so that no cervical sample could be collected at that visit.
- Subjects with normal cervical cytology, but who are oncogenic HPV DNA positive in two subsequent tests, will be referred to colposcopy. The result of the subjects' last HPV-015 study visit will be taken into account at Visit 1.
- Subjects with a single cervical cytology reading of \geq ASC-US (atypical squamous cells of undetermined significance) and positive for oncogenic HPV DNA will be referred to colposcopy.
- Subjects with a single cervical cytology reading of \geq LSIL (low grade squamous intraepithelial lesion) will be referred to colposcopy.

Please note that a missing result for HCII will be managed as oncogenic HPV positive.

In case of referral for colposcopy, the post-colposcopy follow-up strategies are:

- If no lesion is detected or the detected lesion does not require any treatment, subjects will be asked to return at the next study visit.

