9. CHANGES FROM PLANNED ANALYSES

Since SAE is not the endpoints of study protocol, following analysis related to SAE will not be generated

- All fatal SAEs occurring throughout the study period.
- All SAEs assessed as being possibly related to study participation occurring throughout the study period.
- All SAEs assessed as being possibly related to GSK products occurring throughout the study period.
- Withdrawal from the study due to AEs or SAEs

Statistical Analysis Plan	
Study alias & e-track number(s): HPV-062 EXT:015 (113617)	

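### Does the move from per-subject to per-visit summaries in SAP 6.1.2 leave the overall colposcopy-referral figure undefined?

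*SAP*

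**What the plan says.** Protocol 10.6.4 introduces its list of outputs with "For each subject and overall". The referral item reads "Referrals to colposcopy according to management algorithm, if required". SAP 6.1.2 carries over the four clinical-management items under "For each visit and overall", with the referral item cut to "Referrals to colposcopy, if required".

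SAP section 9 records one departure from the protocol: the AE and SAE outputs are dropped, beginning "Since SAE is not the endpoints of study protocol". It mentions neither the change of unit nor the shortened line. Protocol 10.5 says "Any deviation(s) or change(s) from the original statistical plan outlined in this protocol will be described and justified in the final study report", and SAP section 8 repeats this.

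The algorithm in SAP section 2 states that women with normal cytology who are "oncogenic HPV DNA positive in two subsequent tests, will be referred to colposcopy". Where colposcopy finds nothing that needs treatment, "subjects will be asked to return at the next study visit". Protocol Table 1 has referral recorded at each of the four visits. SAP section 4 words all four endpoints as occurrences. SAP section 6 places the analysis on the Total cohort.

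**The concern.** The algorithm text makes no exception for a woman already sent to colposcopy (Figure 3 is not reproduced in the text available). A woman with a persistent infection and nothing to treat could therefore be referred at Visits 1, 2, 3 and 4. With the subject gone from the heading, the overall row might show women ever referred, total referrals, or the share of visits that led to referral. Colposcopy referral is one of four endpoints and lies close to the clinical-management objective, so a reader could misjudge how many women needed work-up.

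The shortened line raises a second question. Sites also try to document colposcopies done outside the study (Protocol 5.5), so it might seem open whether those enter the count. The absence of both changes from SAP section 9 makes the shift look unintended.

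**Working it through.** The plan has no figure to reproduce: Protocol 10.2 does no power calculation, and its 1500 is an expected number. The check has two parts.

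**1. How far the readings can differ.** Neither document gives clearance, treatment or withdrawal rates, so all rates here are assumptions. Take women who are HPV-positive at HPV-015 exit and join at Visit 1. Let infection persist with probability p per year, a share t of referrals end in treatment (which ends participation), and a share w withdraw per year. Every woman ever referred has her first referral at Visit 1, so

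referrals per woman referred = 1 + q + q² + q³, with q = p(1−t)(1−w).

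| p | t | w | q | Women per 100 | Ratio | Referrals per 100 |
|---|---|---|---|---|---|---|
| 0.4 | 0.3 | 0.1 | 0.252 | 40 | 1.33 | 53 |
| 0.4 | 0 | 0 | 0.40 | 40 | 1.62 | 65 |
| 0.6 | 0.2 | 0 | 0.48 | 60 | 1.82 | 109 |
| 0.6 | 0 | 0 | 0.60 | 60 | 2.18 | 131 |
| 0.7 | 0.2 | 0 | 0.56 | 70 | 2.05 | 143 |
| 0.7 | 0 | 0 | 0.70 | 70 | 2.53 | 177 |
| 0.8 | 0 | 0 | 0.80 | 80 | 2.95 | 236 |

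The last row does not fit the protocol. It leaves 0.8² = 64% positive at two years, whereas Protocol 1.2 expects the majority of oncogenic infections to have cleared by then, which needs p below √0.5 ≈ 0.71. A half-and-half mix of p = 0.8 and 0.4 does fit, with (0.64 + 0.16)/2 = 40% positive at two years. It gives 60 women and 151 referrals per 100, a ratio of 2.5. A defensible range for raw counts is therefore about 1.3 to 2.5.

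Percentages differ less, because the visit denominator grows with the referrals:

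- Equal p, no late entry: 60% of women and 60% of visits at p = 0.6, a gap of 0.
- The 0.8/0.4 mix: visits = 118.1/0.8 + 32.5/0.4 = 228.8, and 150.6/228.8 = 66% of visits against 60% of women.
- The same mix with 50% joining late: 58% of visits against 47% of women. This counts the HPV-015 result as the earlier positive whenever a woman joins; SAP section 2 says so only for Visit 1.
- 1500 women, clearance 50/40/30/20% over the visits, 20% of referrals treated: referrals 750 + 360 + 201.6 + 129.0 = 1441, visits 1500 + 600 + 288 + 161.3 = 2549. That is 56.5% of visits (95% CI 54.6–58.5) against 750/1500 = 50.0% of women (47.4–52.6).

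**2. Which reading the documents support.**

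- The protocol's heading also ends in an undefined *overall*. The SAP inherited that gap.
- An occurrence endpoint reads most naturally as whether a woman had the event.
- The cohort in SAP sections 5 and 6 is a set of women.
- SAP 7.1 and 7.2 plan percentages with two-sided 95% limits, and the sole reference in SAP section 10 is the Clopper-Pearson interval. Referrals over women cannot be such a proportion: 131 or 236 per 100 exceeds 100%.
- Treatment referral is the same under either reading, since it ends participation.
- On the shortened line, Protocol 5.8.2.6 defines the recorded item as referral under the algorithm, and the visit-activities list in SAP section 2 repeats this. Protocol 5.5 concerns colposcopies performed, which go in their own eCRF section. That is a different data item from the referral endpoint.

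**The case for a change.** The strongest reply is that none of this is written in SAP 6.1.2. A denominator of visits would also yield percentages below 100, and an exact binomial interval could be computed on it even though repeat visits by one woman are not independent. In the falling-clearance example the two intervals do not overlap although the data are the same.

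By-visit tables would not let a reader recover the per-woman figure. Take 110 women, with 100 tested and 60 referred at Visit 1, and 60 tested and 36 referred at Visit 2. The 10 late joiners mean that 50 of the 60 at Visit 2 are returners, so between 0 and 10 of the 36 are first referrals. Women ever referred could be 60 to 70, or 55% to 64%.

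Section 9 was also evidently used to log departures from Protocol 10.6.4 and left these out.

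All of that is accurate, and a sentence on the unit would have been tidier. But it shows missing detail, not a rule that gives a wrong answer. The per-woman count comes straight from data recorded by woman and visit, and SAP 6.1.2 asks for an overall figure besides the by-visit ones. The omission from section 9 breaches nothing yet, because Protocol 10.5 places the duty to describe and justify changes in the study report.

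**Conclusion.** No change to the plan is needed. The wording differs and section 9 is silent, but the unit of *overall* was open in the protocol too, and the rest of the SAP leads an analyst to women with at least one event over the Total cohort. If someone counted referrals instead, the raw number would be about 1.3 to 2.5 times larger; with a visit denominator the percentage would move by 0 to about 11 points. Those sizes rest on assumed persistence, treatment, withdrawal and late-entry rates, and on repeat referral being allowed as the text reads without Figure 3. The question about colposcopies outside the algorithm falls away, since the recorded referral is already tied to the algorithm. The study is descriptive, with no hypothesis test or power calculation, so no conclusion depends on the point. Writing the definition down would only record what a sensible analyst would do.

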7. STATISTICAL CALCULATIONS

7.1. Derived and transformed data

All CI computed will be two-sided 95% CI.

The following categories for cervical cytology reading will be specified:

- Negative for intraepithelial lesion or malignancy (negative).
 - Negative/HCII negative (Normal/oncogenic HPV negative)
 - Negative/HCII positive (Normal/oncogenic HPV positive).
 - Negative/HCII quantity not sufficient (Normal/QNS).
- Unsatisfactory.
- Atypical squamous cells of undetermined significance (ASC-US).
 - ASC-US/HCII negative (ASC-US/oncogenic HPV negative)
 - ASC-US/HCII positive (ASC-US/oncogenic HPV positive).
 - ASC-US/HCII quantity not sufficient (ASC-US/QNS).
- Atypical squamous cells cannot exclude HSIL (ASC-H).
- Low-grade squamous intraepithelial lesion (LSIL).
- High-grade squamous intraepithelial lesion (HSIL).
- Atypical glandular cells (AGC).
- Invasive malignancy.

Handling of missing data:

Demography

For a given subject and a given demographic variable, missing measurement will not be replaced. Therefore, analysis of demography will exclude subjects with missing measurements.

Statistical Analysis Plan	
Study alias & e-track number(s): HPV-062 EXT:015 (113617)	

7.2. Data presentation description

The following decimal description will be used for the demography and safety analyses.

Display Table	Parameters	Number of decimal digits
All summaries	% of count, including LL & UL of CI	1
Demographic characteristics	Mean, median age	1
Demographic characteristics	SD (age)	1

8. CONDUCT OF ANALYSES

Any deviation(s) or change(s) from the original statistical plan outlined in this protocol will be described and justified in the final study report.

8.1. Sequence of analyses

The final analyses will be conducted when all data are available. This analysis will include the final analysis of Demography and safety. These analyses will be the basis of a Clinical Study Report and will be made available to the investigator(s).

Description	Analysis ID (SDD & CARS sub-folder)
Final Analysis	E1_01

8.2. Statistical considerations for interim analyses

No interim analysis is planned for this study.

9. CHANGES FROM PLANNED ANALYSES

Since SAE is not the endpoints of study protocol, following analysis related to SAE will not be generated

- All fatal SAEs occurring throughout the study period.
- All SAEs assessed as being possibly related to study participation occurring throughout the study period.
- All SAEs assessed as being possibly related to GSK products occurring throughout the study period.
- Withdrawal from the study due to AEs or SAEs

Statistical Analysis Plan	
Study alias & e-track number(s): HPV-062 EXT:015 (113617)	

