8.1. Safety definitions

NOTE: The term AE denotes both non-serious and serious adverse events. In this study, only fatal SAEs, SAEs related to study participation, SAEs related to a concurrent GSK medication and AEs or SAEs leading to withdrawal from the study will be reported.

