9.2. Subject withdrawal

Subjects who are withdrawn because of AEs must be clearly distinguished from subjects who are withdrawn for other reasons. Investigators will follow subjects who are withdrawn as result of an SAE/AE until resolution of the event (see Section 8.4).

Withdrawals will not be replaced.

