9.2.1. Subject withdrawal from the study

From an ‘analysis’ perspective, a withdrawal’ from the study is any subject who did not come back for the concluding visit and who was not discharged from the study, either due to treatment referral or due to having cleared the oncogenic HPV infection.

All data collected until the date of withdrawal/last contact of the subject will be used for the analysis.

A subject is considered a ‘withdrawal’ from the study when no study procedure has occurred, no follow-up has been performed and no further information has been collected for this subject from the date of withdrawal/last contact.

Investigators will make an attempt to contact those subjects who do not return for scheduled visits or follow-up.

Information relative to the withdrawal will be documented in the eCRF. The investigator will document whether the decision to withdraw a subject from the study was made by the subject herself or by the investigator, as well as which of the following possible reasons was responsible for withdrawal:

- Serious adverse event.
- Non-serious adverse event.
- Protocol violation (specify).
- Consent withdrawal, not due to an adverse event.
- Moved from the study area.
- Lost to follow-up.
- Death.
- Other (specify).

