10. DATA EVALUATION: CRITERIA FOR EVALUATION OF OBJECTIVES

10.1. Study endpoints

- Occurrence of positive oncogenic HPV DNA results in cervical samples by HPV DNA testing (Hybrid Capture® II test [HCII]).
- Occurrence of cervical cytological abnormalities in cervical samples by ThinPrep® PapTest.
- Occurrence of referral to colposcopy.
- Occurrence of referral to treatment.

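### SAP section 9 cancels all four AE/SAE outputs planned in protocol 10.6.4, for a reason that was already true when they were planned

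*SAP*

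**What the plan says.** Protocol 10.6.4 (*Descriptive analysis of safety*) lists eight outputs, to be given for each subject and overall. Four are clinical-management results: HPV DNA tests, cytology, colposcopy referrals and treatment referrals. Four are AE/SAE outputs, one of which reads "All SAEs assessed as being possibly related to study participation occurring throughout the study period". The other three are fatal SAEs, SAEs possibly related to GSK products, and withdrawals due to AEs or SAEs.

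Protocol 8.1 limits what the study reports: "In this study, only fatal SAEs, SAEs related to study participation, SAEs related to a concurrent GSK medication", together with AEs or SAEs that lead to withdrawal. Protocol 10.1 lists four endpoints, the last being "Occurrence of referral to treatment". None is an adverse event.

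On withdrawals, protocol 9.2 says "Subjects who are withdrawn because of AEs must be clearly distinguished from subjects who are withdrawn for other reasons", and 9.2.1 says "Information relative to the withdrawal will be documented in the eCRF", with a list of eight possible reasons.

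SAP section 9 (*Changes from planned analyses*) states "Since SAE is not the endpoints of study protocol, following analysis related to SAE will not be generated" and then lists the four AE/SAE items of protocol 10.6.4. SAP 6.1.2 keeps the four clinical-management items. SAP 6.1.1 says "withdrawal status will be summarised using descriptive statistics", without naming reasons. SAP 8.1 still says of the final analysis: "This analysis will include the final analysis of Demography and safety".

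**The concern.** The SAP removes protocol-planned safety output on the ground that SAEs are not endpoints. Safety summaries usually are not endpoints, and the protocol planned these with its endpoint list already fixed. If the SAP is followed as written, the study report has no planned count of deaths or related SAEs. Withdrawals due to adverse events would be visible only if someone chose to break withdrawal status down by reason. The only AE/SAE data the study collects would then be summarised by an unplanned choice, or not at all.

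**Working it through.** No sample size, power or error rate is involved, so the check sets the sections side by side and counts.

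**Step 1: what was planned and what survives.**

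| Output in protocol 10.6.4 | Category reported under protocol 8.1? | In the SAP |
|---|---|---|
| HPV DNA results | not an AE/SAE item | kept, 6.1.2 |
| Cytology results | not an AE/SAE item | kept, 6.1.2 |
| Colposcopy referrals | not an AE/SAE item | kept, 6.1.2 |
| Treatment referrals | not an AE/SAE item | kept, 6.1.2 |
| Fatal SAEs | yes | cancelled, section 9 |
| SAEs possibly related to participation | yes | cancelled, section 9 |
| SAEs possibly related to GSK products | yes (8.1 words it as concurrent GSK medication) | cancelled, section 9 |
| Withdrawals due to AEs or SAEs | yes | cancelled, section 9 |

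Cancelled: 4 of 8 outputs, which is 4 of 4 AE/SAE outputs and 4 of 4 AE/SAE categories reported. SAP sections that define any other AE or SAE table or listing: 0.

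**Step 2: does the stated reason explain the removal?**

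- *Timing.* Of the 4 endpoints in protocol 10.1, 0 is an SAE. SAP section 4 repeats the same four. The SAP's document history cites protocol Administrative Change 1, in which 10.6.4 still stands. The fact given as the reason was therefore already true when the outputs were planned.
- *Consistency.* SAP 6.1.1 keeps demography, withdrawal status and the distribution of subjects by site. None of these is an endpoint, so the SAP does not apply its own rule.
- *Scope.* The fourth cancelled item covers AEs as well as SAEs. A reason about SAEs does not reach non-serious AEs that lead to withdrawal.

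**Step 3: does the withdrawal summary fill part of the gap?** Protocol 9.2.1 records 8 reasons. Three of the 8 (serious AE, non-serious AE, death) carry safety information. SAP 6.1.1 names 0 of the 8. The data would allow a split, but the SAP does not state one. Even with a split, SAEs that did not lead to withdrawal would remain uncounted.

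**Step 4: the rest of the SAP.** Section 2 still says that these event categories will be reported. Section 7.2 sets decimals for safety analyses, and 8.1 includes safety in the final analysis. With section 9 in force, no AE/SAE output stands behind any of these statements.

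**The case against.** The best case for the sponsor has four parts.

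1. **The change is declared.** It sits under the proper heading with a reason, and both documents require changes to be described and justified in the final report. This stands as to openness. It does not repair the justification.
2. **The study is not a safety study.** Protocol 1.2 says it is not meant to gather long-term safety data. There is one group, no study product is given, and events related to the HPV-015 vaccine are reported under HPV-015. This lowers the stakes, because the counts support no comparison. But that purpose was already set when the protocol planned the four outputs, and they concern deaths, study participation, concurrent GSK products and withdrawals, not long-term vaccine safety.
3. **The withdrawal requirement is not a table specification.** Protocol 9.2 is a conduct section, and the eCRF reason codes can satisfy it. Protocol 10.6.1 itself asks only for withdrawal status. This is fair: the loss against the protocol's analysis section is the fourth cancelled item, and a table by all eight reasons goes somewhat beyond what section 10.6 asks.
4. **The word safety in SAP 7.2 and 8.1 may mean the clinical-management results,** since protocol 10.6.4 places them under a safety heading. The lines in SAP section 2 can likewise be read as event reporting. This reading is possible, so those sections are better called unclear than contradictory.

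None of this restores a planned summary of fatal or related SAEs.

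**Conclusion.** The concern holds. The SAP removes 4 of the 8 outputs in protocol 10.6.4, and these are all of its AE/SAE outputs, for a reason that does not account for the removal. No other SAP section replaces them.

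The effect is limited to the planned reporting of safety data. Case-level SAE reporting to the sponsor is untouched, and narratives or listings are not ruled out. No endpoint, cohort or clinical-management estimate changes. The conclusion rests on the text of the two documents alone and assumes that no analysis document outside them plans these outputs. It should be fixed, because the lost items are the only AE/SAE information the study collects and restoring them is cheap.

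**What to change.** 1. Delete the cancellation in SAP section 9.
2. Add a section 6.1.3, *Descriptive analysis of safety*. On the HPV-062 Total cohort, give the number and percentage of subjects and a subject listing for each of the four AE/SAE items in protocol 10.6.4. State that the GSK-products item means the concurrent-medication category of protocol 8.1, if that is the intention.
3. In SAP 6.1.1, preferably tabulate withdrawals by the eight reasons in protocol 9.2.1, with serious AE, non-serious AE and death shown separately. This adds slightly to what protocol 10.6 asks, and the core correction does not depend on it.
4. In SAP sections 2, 7.2 and 8.1, state that safety covers both 6.1.2 and the new 6.1.3.

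The cost is SAP wording, four short summaries with listings and one withdrawal table, all from eCRF data already collected. Some outputs may be empty, but a planned zero is still informative. No protocol amendment is needed, because items 1 and 2 restore what the protocol planned.
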